#### 6.1.10. Subgroups

The following subgroups are defined for this study:

Subgroup	Definition/Levels
Measurable PK at Multiple Timepoints	If a participant randomized to CT1812 has measurable (>BLOQ) CT1812 concentrations at 7 or more post-baseline timepoints at which PK was assessed, then they are included in the subgroup.
	All participants randomized to placebo with CT1812 concentrations BLOQ at all post-baseline timepoints at which PK was assessed are included in the subgroup.
	Analyses will summarize all participants who meet the criteria to be included in the subgroup. It is not of interest to compare participants who meet the criteria for inclusion in this subgroup vs. those who don't.
Sex	Male, Female
MMSE at Baseline	18-21, 22-26
Age	<65,>=65
ApoE Status at Baseline	Positive, Negative.  If genotype ApoE or phenotype ApoE contains E4, then ApoE status is considered Positive. Otherwise Negative.
pTau217 at Baseline	<median,>=Median</median,>
	Median value is determined based on all participants combined (regardless of treatment group). This subgroup is based on plasma biomarker samples (not CSF).
Pre/Post COVID	Pre-COVID: Includes participants who completed or prematurely withdrew from the study prior to March 10, 2020.
	Post-COVID: All remaining participants
Region	US, ex-US (EU + AUS)
Acetylcholinesterase (AChE) inhibitors and/or memantine	Yes: Participant took these medications during the treatment period No: Participant did not take these medications during the treatment period

Subgroup	Definition/Levels
use during the study	The following medications will be considered for this subgroup:
	Any medication containing donepezil (Aricept, Namzaric), rivastigmine (Exalon), galantamine (Razadyne, Reminyl), or tacrine (Cognex) is considered an AChE inhibitor.
	Any medication containing memantine (Namenda, Namzaric) is considered memantine.

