#### **Table 1: Schedule of Events**

		Screen	Base- line													
	Study day(s)	-60 to -1	1	3 (±1)	7 (±2)	14 (±2)	21 (±2)	28 (±2)	42 (±2)	56 (±2)	70 (±2)	90 (±2)	98,126, 154 (±2)	172 (±2)	182 (±2)	210 (±2)
	Visit(s)	1	2	3*	4	5	6*	7	8	9	10		11,12 ,13		14	Safety Follow Up 15
		ening Tes	its													
1	Informed consent	X														
2	Inclusion/Exclusion Criteria	X	X													
3	Demography & Medical History	X														
4	Confirm AD diagnosis	X														
5	MMSE	X	X						X				X (Day 98)		X	
6	Modified Hachinski exam and GDS	X														
7	ApoE Status	X														
8	Optional whole blood sample for future biomedical research	X														
9	Screening Laboratories	X														
			n, Vitals,	ECG, Oth	er											
10	Complete Physical Exam	X	X												X	
11	Brief Physical Exam			X	X	X	X	X	X	X	X		X			
12	Vital signs and weight	X	X	X	X	X	X	X	X	X	X		X		X	X
13	ECG (12-lead)	X	X					X		X			X (Day 98)		X	
14	MRI	X													X	
15	Amyloid PET Scan	X														
	•			•		•	•	•	•	•	•					

AD-ST-33.05 Effective date: 22-Jan-2018 Version Final 2.0 | 23May2024

Version Final 2.0 | 23May2024 Page 11 of 37

			Base-													
		Screen	line													
	Study day(s)	-60 to -1	1	3 (±1)	7 (±2)	14 (±2)	21 (±2)	28 (±2)	42 (±2)	56 (±2)	70 (±2)	90 (±2)	98,126, 154 (±2)	172 (±2)	182 (±2)	210 (±2)
	Visit(s)	1	2	3*	4	5	6*	7	8	9	10		11,12 ,13		14	Safety Follow Up 15
					Lumbar l											
16	Chemistry & hematology	X	X	X	X	X	X	X	X	X	X		X		X	X
17	Serum cystatin C		X	X	X	X			X		X		X		X	X
18	PK and Exploratory Biomarkers Sampling	X EB only	X	X	X	X		X	X		X		X		X	
19	Serum biomarkers	X										X		X		
20	Coagulation testing (PT/INR)	X									X**		X (Day 154)			
21	Optional lumbar puncture (CSF Biomarker Sampling)	X											X (Day 98** *)		X	
22	Urinalysis	X	X	X	X	X		X	X	X	X		X		X	
23	Pregnancy testing	X														
	Cog	nitive, Fu	nctional, a	and Safety	Assessme	nts										
24	C-SSRS	X	X	X	X	X	X	X	X	X	X		X		X	X
25	Cognitive Assessments and ADCS-ADL	X	X						X				X (Day 98)		X	
	ADCS-CGIC		X						X				X (Day 98)		X	
					se Events						_					
26	Concomitant Medications	X	X	X	X	X	X	X	X	X	X		X		X	X
27	Adverse Events Assessment		X	X	X	X	X	X	X	X	X		X		X	X
28	Drug Accountability			X	X	X	X	X	X	X	X		X		X	

AD-ST-33.05 Effective date: 22-Jan-2018 Version Final 2.0 | 23May2024

Version Final 2.0 | 23May2024 Page 12 of 37

Statistical Analysis Plan, Sponsor Cognition Therapeutics, Inc. Protocol Number COG0201 PCN Number COGN187880

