		Screen	Base- line													
	Study day(s)	-60 to -1	1	3 (±1)	7 (±2)	14 (±2)	21 (±2)	28 (±2)	42 (±2)	56 (±2)	70 (±2)	90 (±2)	98,126, 154 (±2)	172 (±2)	182 (±2)	210 (±2)
	Visit(s)	1	2	3*	4	5	6*	7	8	9	10		11,12		14	Safety Follow Up 15
29	Drug Dispensation		X					X		X	X		X			
30	In office dose administration		X	X	X	X	X	X	X	X	X		X		X	

Abbreviations: AD = Alzheimer's disease; ADAS-Cog = Alzheimer's Disease Assessment Scale - Cognition subscale; ADCS-ADL = ADCS-Activities of Daily Living Scale; ADCS-CGIC = ADCS-Clinical Global Impression of Change; ApoE = apolipoprotein E; C-SSRS = Columbia Suicide Severity Rating Scale; ECG = electrocardiogram; GDS = Geriatric Depression Scale; LP = lumbar puncture; MMSE = Mini Mental State Exam; MRI = Magnetic Resonance Imaging scan; NTB = Neuropsychological Test Battery; PET = Positron Emission Tomography scan; PK = pharmacokinetic; PT/INR = prothrombin time and international normalized ratio

- \* Study Visit 3 (Day 3) and Visit 6 (Day 21) will not be performed for participants enrolled in Part C.
- \*\* Only required on Day 70 if the optional LP on Day 98 is planned.
- \*\*\*If a participant and investigator are agreeable, an additional LP may be performed at least 24 hours before the Day 98 visit.

If adequate volume is available, CSF will be stored for future evaluation of biomarkers of target engagement or disease modification. See Laboratory Procedures Manual for sample handling. See Section 11.5 for details. Obtained CSF should be sent for cell counts (white blood cells and red blood cells, with differential if either of the counts is abnormal), CSF protein, and CSF glucose at Screening, Day 98 (optional), and Day 182. If abnormalities are observed at Screening, they should be discussed with the Medical Monitor before randomizing the participant.

- 1. Informed consent must be obtained prior to the participant undergoing any study-specific procedures.
- 2. Review of all criteria detailed in Sections 9.2 and 9.3 of protocol.
- 3. Record demographic information, confirm ethnicity and obtain medical history.
- 4. Confirm AD diagnosis in accordance with McKhann 2011 criteria.
- 5. Mini Mental State Exam and Geriatric Depression Scale.
- 6. Perform Modified Hachinski Exam to screen for vascular dementia.
- 7. ApoE genetic testing is required for all participants.
- 8. Optional whole blood sample (~10 mL) for future biomedical research, including potential genetic analyses.

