#### 5. Analysis Populations

The following analysis populations are planned for this study:

- All Subjects: The All Subjects population includes all participants who sign the ICF and get screened for the study.
- Safety Population (SAF): The Safety Population includes all participants who receive one or more doses of study medication.
- Efficacy Modified Intent-To-Treat Population (mITT): The Efficacy mITT Population includes all randomized participants who receive any amount of study drug and who have a baseline and at least one post-baseline assessment of the ADAS-Cog 11 total score.
- Completers Population (CP): The Completers Population includes all randomized participants who completed the study (i.e., who did not prematurely withdraw). There is no expectation that a participant included in the CP will have attended every single scheduled visit; as long as the participant completed the study, they will be included in the population.
- **Pharmacokinetic Population (PK):** The Pharmacokinetic Population includes all participants in the SAF who had at least one quantifiable concentration of CT1812.

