#### 6.1.3. Multiple Comparisons

Although all of the clinical efficacy analyses for this study are exploratory in nature, the ADAS-Cog 11 least square mean change from baseline analysis is considered the primary exploratory analysis of interest compared to the other clinical efficacy analyses. The primary exploratory analysis of the ADAS-Cog 11 will compare the least square mean change from baseline value for the two active arms combined to the least square mean change from baseline value for the placebo arm at day 182, using a two-sided test at the alpha=0.05 level of significance. If the primary exploratory analysis of the ADAS-Cog 11 is statistically significant, then the following comparisons will be made using the least square mean change from baseline values and the same model as for the primary analysis:

- 1) 300 mg CT1812 versus placebo;
- 2) 100 mg CT1812 versus placebo.

Each comparison will be conducted using a two-sided test at the alpha=0.05 level of significance. This fixed sequence testing procedure will control the overall level of significance for this outcome.

All other clinical efficacy analyses will be conducted using two-sided tests at the alpha=0.05 level of significance. No adjustments will be made for multiple comparisons and all other p-values will be considered nominal.

[figure not shown]

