#### 8. Efficacy Analysis

All efficacy analyses are exploratory in nature. The intent of this plan is to run the analysis of covariance (ANCOVA) model described in section 8.1 at the time of the interim analysis and the mixed-model repeated measures (MMRM) model described in section 8.1 at the time of the final analysis. However, if the MMRM model fails to converge, the ANCOVA analysis (with both observed and observed + LOCF values) will be run in place of the MMRM model for the final analysis. A Day 182 visit will be considered out-of-window if it does not occur between study day 171 and study day 193 (inclusive).

For the final analysis, all efficacy analyses will be run using the mITT population and a subset of the efficacy parameters (ADAS-Cog 11, ADCS-ADL, MMSE, ADCS-CGIC) will be summarized using the Completers Population as a sensitivity analysis.

All figures will be based on the mITT population only. The following figures will be produced for each efficacy parameter (ADAS-Cog 11, ADCS-ADL, MMSE, ADCS-CGIC and the composite z-scores: Cognitive Composite score; Memory Composite score; Attention Composite score; and Executive Function Composite score):

- Line plot of change from baseline values.
- Line plot of least square mean change from baseline values.
- By-participant spaghetti plots of the change from baseline values.

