#### 8.2. Mini Mental State Exam (MMSE)

The MMSE is a brief, screening instrument often used in clinical trials to assess dementia severity. The MMSE assesses several aspects of memory and cognitive functioning including orientation, attention, concentration, comprehension, recall, and praxis. The total possible score is 30, with high scores indicating less impairment.

Descriptive summaries of observed values and changes from baseline in the MMSE total score will be calculated by visit.

Change from baseline for MMSE will be analyzed using the same MMRM model described in Section 8.1, with the MMSE score in place of the composite score.

[figure not shown]
For the interim analysis, an ANCOVA model at each visit will be run using the same effects described in Section 8.1, with baseline MMSE score in place of the composite baseline score. For endpoints where LOCF is used, the analyses will be repeated using only observed data.

For the final analysis, MMSE will be summarized and analyzed for both the mITT Population and the Completers Population. Additionally, the change from baseline in MMSE will be summarized and analyzed for each subgroup defined in Section 6.1.10 using the mITT Population. For the subgroup analysis by ApoE status at Baseline, the APOE covariate will be excluded from the statistical model.

Results for MMSE will be listed.

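### The Measurable PK at Multiple Timepoints subgroup sets a 7-sample minimum on CT1812 and none on placebo, so its contrasts are selected on retention, attendance and exposure in one arm only

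*SAP*

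**What the plan says.** The two entry rules in SAP 6.1.10 differ by arm. CT1812 participants need "measurable (>BLOQ) CT1812 concentrations at 7 or more post-baseline timepoints at which PK was assessed". For placebo: "All participants randomized to placebo with CT1812 concentrations BLOQ at all post-baseline timepoints at which PK was assessed are included in the subgroup". The same entry says that members are not to be compared with non-members, so the contrast left is CT1812 against placebo within the subgroup. SAP 8.8 describes the biomarker subgroup comparisons in that way, for each dose and for the doses pooled.

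The subgroup is used widely. SAP 8.2 states that "the change from baseline in MMSE will be summarized and analyzed for each subgroup defined in Section 6.1.10 using the mITT Population". SAP 8.3, 8.5 and 8.6 do the same for ADAS-Cog 11 and 13, ADCS-CGIC and ADCS-ADL, and SAP 8.8 applies this subgroup to every biomarker.

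The sampling calendar is the row "PK and Exploratory Biomarkers Sampling" in SAP Table 1, with the footnote "Study Visit 3 (Day 3) and Visit 6 (Day 21) will not be performed for participants enrolled in Part C". The mITT population takes treated, randomised participants "who have a baseline and at least one post-baseline assessment of the ADAS-Cog 11 total score"; the first such assessment is scheduled at Day 42. SAP 6.1.3 says that, outside the ADAS-Cog 11 sequence, "all other p-values will be considered nominal". SAP 8 adds that a set of clinical scales "will be summarized using the Completers Population as a sensitivity analysis".

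**The concern.** A minimum number of measurable samples is also a minimum length of stay and a minimum attendance. On CT1812, participants who leave early, miss several visits or take the drug irregularly are removed. Their placebo counterparts stay in. If those people tend to decline differently from the rest, the arms differ at Day 182 even when the drug does nothing.

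The MMRM cannot repair this. It handles missing visits of people who are in the analysis, whereas this rule also discards the observed data of the CT1812 participants it removes. Nothing elsewhere in the SAP sets a placebo minimum or matches the arms on follow-up. At stake is how a favourable result among exposed participants would be read: part of it could be selection, and the planned output could not separate the two.

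**Working it through.** **Scale, from the plan's own power figure.** Inputs (SAP 3.2): 48 per group, 15% dropout, SD 5.4, difference 3.0, two-sided 0.05, pooled CT1812 against placebo. Evaluable: 48 × 0.85 = 40.8 placebo and 96 × 0.85 = 81.6 CT1812. SE = 5.4 × √(1/40.8 + 1/81.6) = 1.04. Power = Φ(3.0/1.04 − 1.96) ≈ 0.83 (0.82 with the t distribution), close to the stated 81%. The documents give no size or power for the PK subgroup.

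**When the seventh sample falls, if none is missed.**
- SAP Table 1, Parts A/B: Days 3, 7, 14, 28, 42, 70, 98, 126, 154, 182. Ten samples; the seventh is Day 98.
- Part C (no Day 3): nine samples; the seventh is Day 126.
- Protocol 11.2 omits Day 3 for everyone, although protocol 10.2.3 and Table 1 include it. On that list all Parts have nine samples and the seventh is Day 126.
- Protocol 10.2.14 makes the Day 182 visit double as the Early Termination visit, with a PK sample. SAP 6.1.6 only lists such visits before Day 170, but it concerns summary tables, not subgroup membership. If a measurable Early Termination sample counts, leaving soon after Day 70 (ten-sample schedule) or Day 98 (nine-sample schedule) can suffice.

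**Attendance and exposure.** Let p be the assumed chance that a scheduled sample is collected and measurable. The chance that a CT1812 completer fails the rule is P(X ≤ 6), with X binomial:

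| p | 9 samples | 10 samples |
|---|---|---|
| 0.95 | 0.8% | 0.1% |
| 0.90 | 5.3% | 1.3% |
| 0.80 | 26% | 12% |

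A placebo completer with the same missed visits stays in.

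**Bias with no true effect.** Simulation of 96 CT1812 against 48 placebo, 62 of 144 in Parts A/B, 6,000 runs in each of 10 scenarios. Early Termination samples were not modelled. Assumptions, none from the documents except the SD of 5.4 at Day 182, the 15% dropout and the group and Part sizes:
- changes at Days 42/98/182 with SD 4.2/4.8/5.4, correlations 0.65 (adjacent) and 0.50;
- dropout logistic in the latest change, slope 0, 1 or 2 per SD, the same mechanism in all arms;
- 3% of samples missed at visits without cognitive testing;
- a collected sample measurable with probability 0.98 (adherent) or 0.50 (non-adherent);
- likelihood-based repeated-measures estimate without covariates; mITT requires Day 42 data.

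Bias in the Day 182 ADAS-Cog difference, in points (negative favours CT1812; Monte Carlo SE 0.013–0.014):

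| Scenario | SAP rule | Placebo minimum of 7 collected | One rule in all arms |
|---|---|---|---|
| 15% dropout, unrelated to outcome | +0.01 | within −0.03 to +0.01 | within ±0.02 |
| 15% dropout, outcome-dependent | −0.18 to −0.30 | within −0.03 to +0.01 | within ±0.02 |
| 25% dropout, outcome-dependent | −0.31 to −0.46 | within −0.03 to +0.01 | within ±0.02 |
| 10–20% non-adherent, declining 2 points more | −0.37 to −0.54 | −0.19 to −0.36 | within ±0.02 |
| 10–20% non-adherent, declining 2 points less | −0.02 to +0.16 | +0.15 to +0.33 | within ±0.02 |

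The two non-adherence rows use 15% dropout with slope 1. With 10% non-adherence and dropout both unrelated to outcome, the SAP rule gives +0.02. Full mITT and Completers stay within ±0.02 throughout. At 15% outcome-dependent dropout the bias is 0.18–0.30 SE, or 6–10% of 3.0 points, and the 5% test rejects in 5.3–6.0% of runs; at 25% it rejects in 5.5–7.3%.

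Separate repeats of the dropout-only scenarios gave −0.17 to −0.30 at 15% and −0.30 to −0.47 at 25%. Counting Early Termination samples cut the 15% figures to about −0.11 to −0.19.

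A second model, with other assumed mechanisms (15% dropout; 8–15% of samples missed or unmeasurable per visit), gave zero when nothing was related to decline, at most about 0.06 points when only dropout was, and about 0.1 to 1.4 points in favour of CT1812 when missed or unmeasurable samples rose with decline.

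**The case against.** The strongest reply is that little rests on this subgroup. The clinical-scale analyses are exploratory with nominal p-values, mITT is the main analysis, and the Completers analysis already conditions on retention alike in all arms. CSF change needs a Day 182 sample whichever arm the participant is in. At the plan's own 15% dropout, the modelled inflation of the 5% test is at most about one percentage point. All of this stands, and it limits the severity. It does not remove the point: the Completers analysis does not cover biomarkers and does not alter this subgroup, nominal p-values concern multiplicity rather than bias, and CSF biomarkers serve the secondary objective, so not every affected analysis is exploratory.

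A second reply is that the subgroup is meant to examine verified exposure, which placebo cannot match. That is fair, and it is why the existing version should be kept and labelled rather than dropped.

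A reader might also infer more than the documents support:
- *That CT1812 participants must stay to Day 98 or Day 126.* The SAP does not say whether Early Termination samples count. A late one may be BLOQ, since protocol 9.5.1 allows two weeks after the last dose.
- *That the threshold is stricter in Part C.* This holds only if Day 3 counts in Parts A/B, on which protocol 11.2 and Table 1 disagree.
- *That the rule necessarily flatters CT1812.* The direction depends on how non-adherers decline.
- *That the primary exploratory ADAS-Cog 11 test is compromised.* It uses the full mITT population and is untouched.

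**Conclusion.** The asymmetry is explicit in SAP 6.1.10 and nothing else in the documents cures it; that part is certain. The size and direction are not. Under the main model's assumptions, bias is about zero if retention and exposure are unrelated to outcome, and roughly −0.1 to −0.3 ADAS-Cog points at 15% outcome-dependent dropout, at the lower end if Early Termination samples count. The second model puts the dropout-only part lower still, at no more than 0.06 points. Non-adherence can make the bias larger or reverse it. Every figure is for ADAS-Cog; the documents give no basis for sizing the effect on plasma biomarkers, where no Completers analysis stands beside the subgroup. The point ranks as minor to should-fix: modest in likely size, but avoidable.

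**What to change.** In SAP 6.1.10, before unblinding:

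1. Beside the measurable-concentration version, run one with a single rule in all arms: PK samples collected at 7 or more post-baseline timepoints, regardless of result. State whether Day 3 and Early Termination samples count. This version still conditions on retention, so it supplements mITT and does not replace it; its near-zero bias assumes the same dropout mechanism in all arms.
2. Label the measurable-concentration version as conditioned on exposure after randomisation and not a randomised comparison.
3. Optionally, add to that version a placebo minimum of 7 collected samples, all assessed values BLOQ. This removes the retention and attendance part. It leaves selection on exposure, and it can increase the bias if non-adherers decline more slowly (from −0.02 to +0.16 up to +0.15 to +0.33 in the table), so it should not be the only change.

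The cost is a few SAP sentences and one extra run on data already collected. The common rule, like the optional minimum, removes about 3 placebo participants at 15% dropout (46.2 − 43.2 = 3.0) or 5 at 25% (44.9 − 39.9 = 5.0). If 20% are non-adherent, the common rule keeps about 86 CT1812 participants, against about 71 under the measurable rule.

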 - a) Low dose lorazepam may be used for sedation prior to MRI scan for those subjects requiring sedation. At the discretion of the investigator, 0.5 to 1 mg may be given orally prior to an MRI scan with a single repeat dose given if the first dose is ineffective. No more than a total of 2 mg lorazepam may be used for the MRI.
 - At the discretion of the investigator, lorazepam or another anxiolytic may be administered as per local standard of care prior to MRI scan or optional lumbar puncture. Note neurocognitive testing should not be done within 24 hours of administration of conscious sedation.
 - b. The stable use of zolpidem or eszopiclone for sleep is allowed.
 - c. Stable use of short-acting benzodiazepines and trazadone, specifically as sleep aids are allowed.
- 14) Any disorder that could interfere with the absorption, distribution, metabolism or excretion of drugs (e.g. small bowel disease, Crohn's disease, celiac disease, or liver disease).
- 15) Nootropic drugs except stable AD meds (acetylcholinesterase inhibitors or memantine).
- 16) Suspected or known drug or alcohol abuse, i.e. more than approximately 60 g alcohol (approximately 1 liter of beer or 0.5 liter of wine) per day indicated by elevated MCV significantly above normal value at screening.
- 17) Suspected or known allergy to any components of the study treatments.

- 18) Enrollment in another investigational study or intake of investigational drug within the previous 30 days or five half-lives of the investigational drug, whichever is longer.
- 19) Intake of drugs or substances potentially involved in clinically significant induction or inhibition of CYP3A4 or P-gp mediated drug interactions with CT1812, within 4 weeks or five half-lives of the interacting drug prior to administration of CT1812 and throughout the course of the study. See Appendix A for a complete list of prohibited substances. See Section 9.3.1 for handling of Paxlovid™ administration for COVID infection during the study.
- 20) Any prior exposure to immunomodulators, anti Aβ vaccines, or Aβ passive immunotherapies for AD (e.g. monoclonal antibodies) and/or exposure to BACE inhibitors within the past 30 days.
- 21) Any vaccination within one week of the baseline visit.
- 22) Any condition, which in the opinion of the investigator or the sponsor makes the subject unsuitable for inclusion.

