10.3 Concomitant Medications and Other Restrictions

All medications mentioned in the exclusion criteria (Section 9.3) are expressly prohibited at any time during the study. Exceptions to the list of excluded medications may be made on a case-by-case basis if discussed and approved by the Medical Monitor in advance. Intake of drugs or substances potentially involved in clinically significant CYP3A4 or P-gp mediated drug interactions with CT1812, within 4 weeks or five half-lives of the interacting drug prior to administration of CT1812 and throughout the course of the study. Grapefruit juice should be avoided in the two weeks prior to dosing and throughout the course of the study. See Appendix A for a list of these prohibited substances.

Participants may be on stable doses (at least 30 days prior to screening) of an acetylcholinesterase inhibitor and/or memantine and continue these medications during the study. Participants may be on a stable dose (at least 60 days prior to screening) of an SSRI antidepressant and may continue this medication during the study.

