Participants who initially do not meet all enrollment criteria for this study may be permitted to re-screen. Re-screening may be permitted on a case-by-case basis following a discussion between the Principal Investigator (PI) and the Medical Monitor regarding whether a participant remains potentially eligible to participate in the study. A participant who is re-screened is not required to sign another ICF if the re-screening occurs within 30 days from the previous ICF signature date. There is no minimum period of time a participant must wait to re-screen for the study. The participant must meet all eligibility criteria at the time of re-screening in order to qualify for the study. Depending upon the time from the last screening visit, the Medical Monitor will determine what assessments need to be repeated.

The study start date is defined as the date on which the first Informed Consent is signed. A participant is considered to have completed the study if he/she has completed all study visits. The end of the study is defined as the date of the last visit or the date of the last procedure of the last participant in the study.

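### The Pre/Post-COVID subgroups are split by date of completion or withdrawal, so for participants first dosed from about 14 August 2019 to 9 March 2020 early withdrawal decides the stratum

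*SAP*

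**What the plan says.** The subgroup table in SAP 6.1.10 gives the Pre-COVID level as: "Includes participants who completed or prematurely withdrew from the study prior to March 10, 2020". All remaining participants are Post-COVID. SAP 3.1 fixes what completion means: "A participant is considered to have completed the study if he/she has completed all study visits". By SAP Table 1 the last visit is the Day 210 safety follow-up, and the last cognitive and functional testing is at Day 182.

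The acetylcholinesterase-inhibitor/memantine level in the same table is Yes when this holds: "Participant took these medications during the treatment period". By contrast, the table anchors MMSE, ApoE status and pTau217 at baseline.

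SAP 8.2, 8.3, 8.5 and 8.6 analyse MMSE, ADAS-Cog 11 and 13, ADCS-CGIC and ADCS-ADL in every subgroup of that table, in the mITT population. SAP 8 calls all efficacy analyses exploratory. SAP 6.1.3 treats p-values outside the ADAS-Cog 11 sequence as nominal.

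**The concern.** Randomisation makes the arms comparable within a subgroup when membership is settled before treatment starts. Here, for participants under way when the pandemic date arrived, membership depends on whether they had already withdrawn. Withdrawal is something treatment can affect, through tolerability or through decline. If the arms lose different kinds or numbers of participants, those added to Pre-COVID and removed from Post-COVID differ by arm too.

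The Pre-COVID stratum is likely to be small, so a few such participants weigh heavily in it. The minimum of 10 participants per group in SAP 8.8 is written for the biomarker subgroups. No such floor is stated for the clinical endpoints, so a very small stratum could still be analysed and reported.

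The rule also fits its apparent purpose loosely. A participant first dosed from 14 August to 10 September 2019 has every planned efficacy visit before 10 March 2020, yet is Post-COVID if he or she stays, because only the safety follow-up falls later.

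**Working it through.** **Inputs.** Cut date 10 March 2020 (SAP 6.1.10). Last visit Day 210 and last efficacy visit Day 182 (SAP Table 1). Parts A and B are the first 62 participants, Part C is everyone enrolled after October 2021, and up to 144 are planned (Protocol synopsis, SAP 3.1). 48 per arm, SD 5.4, difference 3.0, dropout 15%, pooled active versus placebo (SAP 3.2).

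**The plan's own figure.** The plan states none for these subgroups. The nearest is the 81% power, which supplies the SD and dropout used below. After 15% dropout the groups are 40.8 and 81.6. SE = 5.4 × √(1/40.8 + 1/81.6) = 1.035, and 3.0/1.035 = 2.897. Power = Φ(2.897 − 1.960) = 82.6%. With 40 and 80 it is 81.8%, or 81.2% from the t distribution. The stated figure is reproduced closely enough.

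**Dates.** Day *d* falls *d* − 1 days after Day 1.
- Day 210: 13 August 2019 + 209 days = 9 March 2020.
- Day 182: 10 September 2019 + 181 days = 9 March 2020.
- Window in which withdrawal decides the label: 14 August 2019 to 9 March 2020, 209 days or about 30 weeks. The ±2-day visit tolerance moves its start by the same amount.

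| Day 1 | Withdraws before 10 March 2020 | Does not |
|---|---|---|
| Up to 13 August 2019 | Pre | Pre (all visits done) |
| 14 August 2019 to 9 March 2020 | Pre | Post |
| From 10 March 2020 | cannot occur | Post |

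**How many can be affected.** With full enrolment, 144 − 62 = 82 participants are in Part C and are Post-COVID whatever they do. Even if all 62 others fell in the window, 15% dropout gives 0.15 × 62 = 9.3 withdrawals, not all of them before the cut.

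**Size under assumptions.** Three-visit trials were simulated and analysed by maximum likelihood equivalent to an unstructured MMRM, with SD 5.4 and, except where the arms were made to differ, about 15% dropout. Enrolment (5 to 24 participants before the window, 10 to 38 within it), correlations and dropout mechanisms are assumptions. About 0.7 to 4 participants per trial change stratum. The dropout share of Pre-COVID rises from about 14–22% to 20–33%, and to 40–53% with 5 before and 30 within the window. The shift in the Day 182 difference, compared with classifying the same trials by Day 1 date, is:

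| Dropout mechanism | Pre-COVID | Post-COVID |
|---|---|---|
| Same in both arms | none detectable | none detectable |
| 10% placebo, 25% active, decliners leave | 0.1 to 0.3 point | 0.01 to 0.03 |
| Decliners leave on placebo, non-decliners on active | 0.2 to 0.4; about 1.0 in the 5/30 case | 0.02 to 0.1 |

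The direction depends on the mechanism. Monte Carlo error in the small Pre stratum is about 0.1 to 0.2 point.

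**Medication subgroup.** If nobody starts these drugs during treatment, the shift is zero. If 7–24% of non-users start because of decline (assumed, with 40–80% on treatment at baseline), it is still zero when CT1812 has no effect. With a true 3-point effect, the No level is attenuated by about 0.2 to 0.4 point and the Yes level shifts by about 0.03 to 0.2.

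**The case against.** The strongest reply has four parts.

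First, for most participants the COVID label follows from entry date alone: Part C is always Post, and so is anyone first dosed from 10 March 2020. That is right, and it confines the problem to a 30-week window.

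Second, the reclassified participants carry little data. Under SAP 6.1.6 an early-termination visit before Day 170 is only listed, so most of them supply Day 42 and Day 98 values at best. This limits the damage but does not remove it, because the MMRM uses those visits.

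Third, the rule has a readable meaning: Pre-COVID participants spent no study time on or after the cut date. A rule on planned Day 210 by Day 1 date keeps nearly that meaning without using withdrawal.

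Fourth, a reader might infer that cognitive decline decides membership of the medication subgroup, through drugs started on study. The protocol does not support this. Protocol 10.3 says: "Participants may be on stable doses (at least 30 days prior to screening) of an acetylcholinesterase inhibitor and/or memantine and continue these medications". Exclusion 15 in Protocol 9.3 bars nootropic drugs other than stable Alzheimer's medication, and 10.3 adds: "All medications mentioned in the exclusion criteria (Section 9.3) are expressly prohibited at any time during the study". New starts are left to deviations or to this route: "Exceptions to the list of excluded medications may be made on a case-by-case basis if discussed and approved by the Medical Monitor in advance". Use during treatment should therefore nearly equal use on Day 1. This part of the objection stands, and the medication definition is only a wording matter.

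**Conclusion.** The Pre/Post-COVID definition uses post-randomisation information and should be changed. For participants first dosed from about 14 August 2019 to 9 March 2020, early withdrawal selects Pre-COVID. This enriches that stratum with dropouts and can bias its treatment comparison.

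A reader might go further and conclude that both subgroup analyses are biased. The documents do not support that. Bias in the COVID split needs dropout that differs between arms in amount or kind. Bias in the medication split needs on-study starts, which the protocol does not foresee, together with a real drug effect.

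In the scenarios tried, the Pre-COVID shift was mostly under 0.5 point, against the 3.0 points used for sample size, and the Post-COVID shift was 0.1 or less. Those figures rest on assumed enrolment and dropout patterns. The documents give neither enrolment by date nor dropout by arm, so the actual size is unknown. The analyses are exploratory and leave the ADAS-Cog 11 testing sequence untouched. Priority is low to moderate.

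**What to change.** In SAP 6.1.10, define the COVID period by Day 1 (randomisation) date. One choice is Pre-COVID when planned Day 182, the last efficacy visit, falls before 10 March 2020, meaning Day 1 on or before about 10 September 2019; all later entries are Post-COVID. The small downside is that participants with Day 1 from 14 August to 10 September 2019 who stay in the study move from Post to Pre. Using planned Day 210 instead (Day 1 on or before 13 August 2019) avoids that move. Either rule makes membership independent of withdrawal.

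As a secondary change, define acetylcholinesterase-inhibitor/memantine use by status on Day 1, in line with the baseline-anchored subgroups in the same table. It matters only for approved exceptions or deviations.

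The cost is two definitions and their programming. Day 1 dates and concomitant medications from screening are already collected, and sample size and stated power do not change.
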